## Examination of First and Second Generation E-cigarettes

### **Addendum**

#### **COVID-19 Related Procedures**

Due to the COVID-19 pandemic, processes and procedures have been implemented to help protect participants and research staff. These processes and procedures are to be followed as long as social distancing requirements are necessary for conducting study visits.

Only one study participant per study coordinator will attend study visits at the CTR at any given time. All study participants will be provided with a face mask upon entry. Only one coordinator will meet the participant at their car for a temperature check, direct the participant into the building, and the two of them will ride the elevator to the 4th floor physically distanced at least 6 ft apart, both wearing masks. No more than 2 persons may ride the elevator at any given time. The participant will be immediately escorted to a private exam/draw room. Therefore, there will be no waiting in open lobby/waiting areas.

When in the exam room, the study coordinator will stand at least 6 feet away from the study participant to give instructions. Afterwards, the study coordinator will leave the exam room to allow the study participant to conduct the instructed procedures. The study coordinator and study participant will be at least 6 feet away from one another and wearing protective masks at all times during each visit.

Each study coordinator will have a designated exam/draw room and smoking room in which to conduct their designated research study. Each smoking room is separated from the staff control station in the hallway by its own door and contains a large window for the study coordinator to be able to see in and monitor study participant activity within the room. There is also a speaker and microphone system within each smoking room along with the Genetech software system on the outside of each room at the smoking room computer stations. Therefore, the study coordinator and study participant can communicate without being in the room together.

For study measures which cannot be physically distanced, appropriate PPE will be worn at all times by research staff during these procedures including goggles, face masks, gloves, and isolation gowns or lab coats.

Study surveys that are able to be completed remotely will be sent to participants using their preferred method of contact prior to the scheduled in-lab study visit. Surveys will be considered complete if at least 90% of survey responses recorded are valid. Repetitive use of "Refuse to Answer", "0" or skipping of questions are not considered valid. Surveys completed remotely will be checked by research study staff. To receive the study visit portion of compensation, 90% of the survey responses recorded must be valid.

After each participant visit is complete, there will be at least a 45-minute period for cleaning and air exchanges in the negative pressure rooms and for cleaning exam rooms and equipment before the next participant visit. All smoking rooms are under negative pressure with a ventilation rate of 36.8 – 44.1 air changes per hour (ACH).

Examination of First and Second Generation E-cigarettes

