#### **Retention**

All participants will receive \$5 per visit to offset travel costs except those who utilize Lyft transportation services provided at no cost by the research team to and from the study site for 8 visits (\$40), receive \$7, when applicable, for parking, \$40 for visit 1 and \$20 for each subsequent visit after that in which they attend (\$180), an additional \$20 for visits when specimens are collected (\$100), \$1 for each online diary entry (\$105 possible) and an additional bonus up to \$100 for protocol compliance (attending  $\geq$  7 visits and completing  $\geq$ 70% of online daily diary entries, and returning study products) for a total up to \$505. The bonus payment will be given at different time points to encourage participant engagement: \$5 will be given at weeks 1, 4, 8, and 12 if the participant returns their study product for a total of \$20 and the remaining \$20 will go towards their bonus of completing their product phase at their week 12 visit. To receive the \$5 that went towards the completion of the product phase at weeks 1, 4 and 8 visits, participants will need to attend the week 12 visit. The remaining \$40 will be compensated at week 52 if the participant attended  $\geq$  7 visits and completed  $\geq$ 70% of online daily diary entries. If an entire study visit is not able to be completed, the participant will be compensated \$5 for travel and, if applicable, \$7 for parking. We will also facilitate study visits by offering evening and weekend appointments as well as additional retention strategies (e.g., multiple sources of contact, reminder calls/texts/emails). To improve engagement and retention of study participants, participants will receive reminder calls in addition to email or text reminders. Reminders will be sent by text or email based on a participant's preferred method of contact. The participant's preferred method of contact for communication will be observed; however, alternative methods may be employed if issues arise with the preferred method (e.g., participant has run out of minutes; cellular providers are not compatible). These methods are consistent with our team's previous studies and have resulted in excellent retention rates.

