## Outcome Measures

The following outcome measures will be assessed during study visits or emailed to the study participant if they are not able to attend a visit: 1) Complete Substitution will be defined as ≥7 days of no more than 1 conventional cigarette smoked (assessed via the *Timeline Follow Back Questionnaire* that assesses all tobacco/nicotine products used for prior 7 days), exhaled carbon monoxide of <4ppm (see biomarker measures below), and reported use of ECs over the same 7-day period; 2) EC Dependence will be assessed using an adapted version of the *Cigarette Dependence Scale* and the *Penn State EC Dependence Scale*; 3) Cigarette Dependence will be measured with the *Cigarette Dependence Scale*; 4) EC Likeability/Preference will be measured using items derived from the *Cigarette Evaluation Scale* (7-point Likert-type scale assessing different dimensions of responses to EC (e.g., psychological reward, satisfaction, and averseness) and an EC adapted version of the *Product Evaluation Scale*; 5) EC Abuse Liability will be assessed using both the *Drug Effects/Liking Questionnaire* as well as the *Cigarette Purchase Task* (modified to assess amount willing to pay across similar units of product, "How much would you be willing to pay for...a pack of your usual brand of cigarettes?...one e-cigarette cartridge?...1mL of e-liquid?"); 6) Transitions to other style of EC and tobacco products will be assessed by asking participants, "Have you tried any other e-cigarette devices since your last visit?" Affirmative responses will be followed-up with questions regarding type of product, frequency and duration of use; 7) Motivation Rulers: importance, confidence, and readiness to quit smoking and to quit all nicotine products (6-items total) will be collected to assess for changes in motivation over time.

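### The remote-survey validity rule counts repeated 0 answers as invalid and ties the visit payment to validity, with no exemption for truthful zeros

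*Combined protocol and SAP*

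**What the plan says.** The addendum on COVID-19 procedures sets the rule for remote surveys:

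- Scope: "Study surveys that are able to be completed remotely will be sent to participants using their preferred method of contact prior to the scheduled in-lab" visit. The surveys covered are not listed.
- Completeness: "Surveys will be considered complete if at least 90% of survey responses recorded are valid".
- What is not valid: "Repetitive use of 'Refuse to Answer', '0' or skipping of questions are not considered valid".
- Check: "Surveys completed remotely will be checked by research study staff". No criteria for the check are given, and the protocol does not define how many zeros are repetitive.
- Payment: "To receive the study visit portion of compensation, 90% of the survey responses recorded must be valid". Under Retention, attendance is paid at USD 40 for visit 1 and USD 20 "for each subsequent visit after that in which they attend".
- Duration: "These processes and procedures are to be followed as long as social distancing requirements are necessary for conducting study visits". No end date is given.

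Under Outcome Measures, the cigarette component of complete substitution is "≥7 days of no more than 1 conventional cigarette smoked", taken from a Timeline Follow-Back that covers every tobacco and nicotine product over the previous 7 days. The endpoint also needs exhaled CO below 4 ppm and reported e-cigarette use over the same 7 days. The same section allows outcome measures to be emailed to participants who cannot attend. The Power Analysis section names complete substitution, LWD against HWD, as the primary outcome.

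**The concern.** Refusals and skipped items are signs of a poor response. A zero on a use item is often the correct answer. A participant who has stopped smoking truthfully reports zero cigarettes day after day. A smoker who does not vape truthfully reports zero e-cigarette use. The rule puts these answers in the same class as non-response.

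The payment link makes this more than a labelling problem. A participant can avoid refusing or skipping and still answer honestly. A participant with nothing to report can avoid zeros only by entering something untrue. If the false entry is a cigarette count above the endpoint's limit, a success becomes a failure. A CO reading below 4 ppm does not reverse that, because all components are required.

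The Missing Data section would not clearly repair the loss if failing surveys were treated as missing. Its weights model missingness from baseline covariates and previous outcomes, whereas here missingness would depend on the current answers. Weighting also cannot correct a value that was entered falsely.

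**Working it through.** **1. Do truthful zeros exceed the 10% allowance?** The documents do not give the layout of the Timeline Follow-Back. Assume a grid of 7 days by k product rows, with each product that is used being used every day. The share of zero cells is (k − 1)/k for someone using one product and (k − 2)/k for a dual user.

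| k (assumed) | One product only | Dual user |
|---|---|---|
| 2 | 1/2 = 50% | 0% |
| 3 | 2/3 = 67% | 1/3 = 33% |
| 5 | 4/5 = 80% | 3/5 = 60% |

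If each zero counts as invalid and the test is applied to this instrument alone, an exclusive user fails at every k shown. The share is the same for an exclusive vaper and an exclusive smoker. Dual users are penalised less, but they are not exempt: at k = 3 or 5 they fail as well.

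**2. Does a longer survey dilute this?** Yes. If the 90% test covers a whole set of questionnaires, Z zeros pass once the total number of responses is at least Z/0.10. For an exclusive user, k = 2 gives 7 zeros and needs 70 responses; k = 3 gives 14 zeros and needs 140. The protocol states neither the item counts nor whether the test is per instrument or per set.

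**3. Does success require zeros?** If the one-cigarette limit is a 7-day total, at least 6 of 7 daily entries (6/7 = 86%) are zero for every success. If it is per day, zeros are not required, although anyone who has stopped smoking still reports them. The text does not settle which is meant.

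**4. The planned power.** Inputs from Power Analysis: 15% (LWD) and 30% (HWD), two-sided 0.05, 20% attrition, 453 enrolled, 363 evaluable (363/3 = 121 per arm). With a pooled null variance and p̄ the mean of the two rates:

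power = Φ{[d√n − 1.96√(2p̄(1 − p̄))] / √(p₁(1 − p₁) + p₂(1 − p₂))}

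= Φ{[0.15 × 11 − 1.96√(2 × 0.225 × 0.775)] / √(0.1275 + 0.21)} = Φ{(1.650 − 1.157)/0.581} = Φ(0.848) = 0.802.

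This reproduces the stated 80%. The required number is 121 per arm, and 121/0.80 = 151.25, which agrees with 151 per group.

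**5. Sensitivity, by assumption only.** Let a share q of true successes be lost in both e-cigarette arms across the whole trial.

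- *Counted as failures:* the rates become 15(1 − q)% and 30(1 − q)%, with 121 per arm.
- *Treated as missing:* the LWD rate is 0.15(1 − q)/[0.15(1 − q) + 0.85] on 121 × [0.15(1 − q) + 0.85] participants. The HWD rate uses 0.30 and 0.70 in the same way.

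| q | Rates, as failures | Power | Rates, as missing | Power |
|---|---|---|---|---|
| 0 | 15.0% v 30.0% | 0.802 | 15.0% v 30.0% | 0.802 |
| 10% | 13.5% v 27.0% | 0.746 | 13.7% v 27.8% | 0.768 |
| 20% | 12.0% v 24.0% | 0.683 | 12.4% v 25.5% | 0.727 |

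**6. How much of the trial could be exposed?** Under Recruitment, 220 of the 453 had already been recruited in Oklahoma and 233 were still to come from Columbus. The addendum describes visits at one centre. If only the Columbus participants are exposed, which is an inference, a trial-wide q of 10% to 20% needs a loss among them of 0.10/(233/453) = 19% to 0.20/(233/453) = 39%.

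**The case against.** The strongest reply is that this is a screen for careless, uniform answering, applied by staff and limited to the distancing period. Listed beside refusals and skips, a repetitive zero can naturally be read that way. That is probably the intention, but the wording does not say so: it gives no criterion and no exemption, and payment depends on it.

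Several stronger readings are tempting, and the documents do not support them.

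- *The rule removes primary-endpoint successes.* A reader might infer this, but the rule governs completeness and payment. Nothing says that failing surveys are deleted, recoded or counted as failures, and Missing Data does not mention the rule. A loss of zero is consistent with the text.
- *The HWD advantage shrinks.* Exclusive smokers in the e-cigarette arms, who are failures, enter as high a share of zeros as exclusive vapers. If failing surveys became missing, both kinds would be lost, and the direction of any bias is open.
- *Every complete switcher must enter repeated zeros and so fail.* This needs the 7-day-total reading of the cigarette limit and a test applied to a short instrument. A success also has non-zero e-cigarette entries.
- *Cigarettes per day is distorted in the same way.* That outcome comes from the daily diary, which is paid separately at USD 1 per entry. The documents do not show that the rule reaches it.

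It also stands that the Timeline Follow-Back is not named among the remote surveys. Emailing of outcome measures is permitted when a visit is missed, and the addendum lists no exclusions, so coverage is plausible rather than documented.

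**Conclusion.** The concern holds as a defect in a stated rule. As written, truthful zeros can make a remote survey incomplete and cost the participant the visit payment, and the way to avoid this is to enter a false non-zero value. If the Timeline Follow-Back is covered, that incentive acts on a component of the primary endpoint and bears more heavily on exclusive use of either product than on dual use.

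A resulting bias is not shown. Its size and direction between LWD and HWD depend on how staff apply the rule, on which surveys and how many items it covers, and on what happens to failing surveys, none of which is stated. The power range of 0.75–0.68 (as failures) or 0.77–0.73 (as missing), against 0.80 planned, illustrates a trial-wide loss of 10% to 20% of successes in both arms and is not an estimate. The point is worth correcting before analysis because the repair is simple.

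**What to change.** Amend the addendum so that:

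- 0 is a valid response on every use or quantity item, at least in the Timeline Follow-Back and the e-cigarette use items;
- refusals and skipped questions remain the validity test;
- no numeric use value decides payment;
- surveys with truthful zeros are kept in the analysis.

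Then re-check any remote surveys already marked incomplete because of zeros and restore them.

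The cost is a short amendment and a check of stored records; sample size and planned power do not change. The downside is that a few careless all-zero surveys will be accepted. CO measured at the in-lab visit still tests reported smoking.
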